#### **3.6.3.2 Sensitivity analyses**

- The best case scenario will consist in deleting patients without data at M6 and M12 (if M12 is available then M12 will be imputed at M6).
- The worst case scenario will consist in imputing a total loss of hearing (score = 0%)
- Tipping point analysis approach will be applied to assess the rules which overturn the conclusion. The steps going from the best scenario to the worst one (all missing scores are 0) and including rules of the primary analysis as intermediary step will be described in the SAP.

### **3.6.4 Futility/Safety Interim Analysis**

Interim analyses will be performed on the safety endpoint. This is based on real-time information given by the monitoring and ECRF.

The trial could be stopped prematurely if the cumulated number of major complications is beyond the worst case scenario reported in the literature. Indeed, literature data reported a weighted average of  $7.1\pm2.0\%$  major complication rate over many years of experience [16,17,18,19,20,21]. Consequently if the number of observed major complication as described in section 3.5.5.2 is beyond  $(7.1\%+2\%)*55= 5$  cases the study should be stopped prematurely for safety reason.

Actually at the 5th major complications during the inclusion period, the DSMB will meet expressly to decide how to move forward on the benefit-risk balance change (e.g. protocol amendment, temporary halt or early termination).

Once the inclusion period is over, the study will go to the end and the complications gather in the safety final report.

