Study planning	
Start date: January 2017
 
Inclusion period: 23 months
 
Running period: 14 months (1 month eligibility period + 13 months postoperative follow-up)
 
Completion date: December 2019

Number of subjects planned	39 English-speaking subjects to assess the primary endpoint with additionally 16 non-English (8 Danish and 8 French) speaking

	subjects to assess safety. In case of shortage of recruitment in a given language recruitment can be increased in another language provided that a minimum of 5 French and 5 Danish speaking patients should be implanted.
Number of centers	5 in Canada, 1 in Denmark
Statistical analysis	Primary efficacy analysis based on the English speaking patients the primary efficacy endpoint (change from baseline to M6 of the HINT-Q) and a one sample t test. Mixed Model for repeated measures with appropriate contrasts.

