## 2.5 Anticipated duration of the clinical investigation

Start date: January 2017

Inclusion period: 23 months

Running period: 14 months

Completion date: December 2019

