**3.5.6 Permitted visit window periods**

Visit	Visit interval (defined as number of weeks relative to visit 3, baseline)	Visit window (defined as number of days from previous visit indicated plus and/or minus day stated)	Visit window (defined as a range in days from previous visit indicated)
1	-8	NA	NA
2	-4	28 days from visit 1 (-25 to +14 days)	3-42 days from visit 1
3	0	28 days from visit 2 (+/- 14 days)	14-42 days from visit 2
4	+2	14 days from visit 3 (-7 to +6 days)	7-20 days from visit 3
5	+4	28 days from visit 3 (-3 to +6 days)	25-34 days from visit 3
6	+16	112 days from visit 3 (-7 to +6 days)	105-118 days from visit 3
7	+28	196 days from visit 3 (-7 to +6 days)	189-202 days from visit 3
8	+52	364 days from visit 3 (-7 to +6 days)	357-370 days from visit 3

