### **3.6.5 Data and Safety Monitoring Board**

Each SAE will be submitted to the DSMB.

If more than 4 major complications are reached during the inclusion period, an extraordinary meeting of the DSMB will take place within the 7 calendar days.

The DSMB shall be notified each time an SAE occurs. Monitoring of key safety endpoints will be conducted as described above, and if rates significantly exceed pre-set thresholds, Competent Authorities will be notified and information supplied to the DSMB.

DSMB's Policies are described in the Oticon Medical Manual Procedures (composition/organization).

The data safety monitoring plan, describe:

- Type of data or events captured under the monitoring plan
- Names of persons who will be responsible for monitoring the data collected
- The frequency of assessments/analysis of data or events captured by the monitoring plan (e.g. periodic time interval, or after a specific number of participants are enrolled)
- Time frame for reporting unanticipated issues, adverse effects, protocol deviations, protocol violations
- Definition of specific events or stopping rules dictating when some actions are required
- Procedure and timeframes for communication outcomes of monitoring reviews to investigator sites, EC and CAs.
- Plans to monitor adherence to the EC/CA-approved protocol and assure the validity and integrity of data.

The DSMB should also assess the performance of overall operation study.

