### **3.6.6 Early Stopping Rules**

No statistical stopping rule for success is applied for the primary efficacy endpoint.

If no interim analysis shows safety endpoint values greater than the pre-set limit, the study shall continue until completion (Please refer to section 3.6.4).

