### **3.6.7 Study Interruption or Withdrawal**

Premature termination of this clinical trial may occur because of regulatory authority decision, change in opinion of the EC/CA, safety problems, or at the discretion of Oticon Medical. In addition, Oticon Medical retains the right to discontinue the trial at any time.

If a trial is prematurely terminated or discontinued, Oticon Medical will promptly notify the PI. After notification, the PI must contact all participating subjects within 24 hours. As directed by Oticon Medical, all trial materials must be collected and all CRFs completed to the greatest extent possible.

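### The required DSMB meeting on the major-complication count can be triggered only while inclusion is open, although the endpoint covers each patient's first year and the limit is computed on all 55 patients

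*Protocol*

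**What the plan says.** Protocol section 3.6.4 opens with a cumulative count of major complications that could stop the trial and gives that count no end date. The limit comes from the literature rate plus its spread, applied to all 55 patients. The section then says that the DSMB meets expressly at the fifth major complication occurring while inclusion is open. Possible outcomes include amending the protocol, pausing, or ending the study early. It closes: "Once the inclusion period is over, the study will go to the end and the complications gather in the safety final report".

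Section 3.6.5 carries the same time limit: "If more than 4 major complications are reached during the inclusion period, an extraordinary meeting of the DSMB will take place", within seven days. The same section also says, without a time limit, that every SAE goes to the DSMB. It adds that key safety endpoints are monitored, with authorities notified and the DSMB informed if rates significantly exceed thresholds. That last clause refers back to the preceding text, so its duration is unclear.

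Section 3.6.6 reads "If no interim analysis shows safety endpoint values greater than the pre-set limit, the study shall continue until completion" and refers the reader to 3.6.4. Section 3.6.7 states a general power: "Premature termination of this clinical trial may occur because of regulatory authority decision, change in opinion of the EC/CA, safety problems", or at the sponsor's discretion.

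The safety co-primary endpoint (section 3.6.1.1 b) is major complications over the first year. The planning figures are "Start date: January 2017", "Inclusion period: 23 months", completion in December 2019, and "Running period: 14 months (1 month eligibility period + 13 months postoperative follow-up". The visit-window table (section 3.5.6) places Visit 8 at "364 days from visit 3 (-7 to +6 days". The SAP has no section on interim safety review.

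**The concern.** The period in which the meeting can be triggered does not match the endpoint it protects. A limit of five in 55 is scaled to the whole sample, but counting towards the meeting stops before many patients have completed the year over which the endpoint is measured. If the fifth major complication falls the day before inclusion closes, the DSMB must meet within a week. If it falls the day after, no meeting is required, although the implanted patients are the same.

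Stopping enrolment is pointless by then, but the outcomes listed in 3.6.4 are wider than that. A protocol amendment can still affect patients who are attending visits. Section 4.2 lists events that need not occur at surgery, such as electrode migration after surgery, extrusion, internal device failure and magnet displacement. It also lists unforeseen complications of long-term implantation. At stake is whether a cluster of such events must be considered collectively, with a decision, while patients are still under study follow-up.

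**Working it through.** **The plan's own figure.** (7.1% + 2%) × 55 = 0.091 × 55 = 5.005. The limit of five is reproduced, and it uses all 55 patients.

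**Calendar check, without an accrual model.** Twenty-three months from January 2017 end with November 2018. Completion is December 2019, so about 13 months of the trial lie outside the trigger. (23 + 14 = 37 months, whereas January 2017 to December 2019 is 36 inclusive. The dates fit 23 + 13 or 22 + 14, and both are covered below.)

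**Share of follow-up after closure, base case.** Inputs: 23 months of inclusion, surgery one month after inclusion, 13 months of follow-up after surgery (Summary; section 2.5). Assumption: uniform accrual, since the documents give no accrual pattern. A patient included at month u has surgery at u + 1 and is followed to u + 14. Post-operative follow-up after month 23 is:

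- 0 for u < 9
- u − 9 for 9 ≤ u ≤ 22
- 13 for u > 22

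Share of follow-up = (13²/2 + 13 × 1) / (23 × 13) = 97.5/299 = 32.6%.
Share of patients with follow-up left = (23 − 9)/23 = 14/23 = 60.9%, about 33 of 55.

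**Schedule variants, uniform accrual.**

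| Variant | Follow-up after closure | Patients with follow-up left |
|---|---|---|
| Base case | 32.6% | 60.9% |
| Inclusion counted at surgery, 13 months | 6.5/23 = 28.3% | 13/23 = 56.5% |
| Visit 8 at 52 weeks (about 12 months), 1-month lag | 84/276 = 30.4% | 13/23 = 56.5% |
| Visit 8 at 52 weeks, no lag | 6/23 = 26.1% | 12/23 = 52.2% |
| 14 months counted from inclusion | 7/23 = 30.4% | 14/23 = 60.9% |
| 22-month inclusion, base schedule | 97.5/286 = 34.1% | 14/22 = 63.6% |

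The range is 26–34% of follow-up and 52–64% of patients.

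**Accrual shape, base schedule.** With linearly declining accrual, the share of patients is (14/23)² = 37% and the share of follow-up is 13%. With linearly rising accrual, they are 1 − (9/23)² = 85% and 52%. Combining accrual shape with the schedule variants widens the extremes to 9% and 27% at the low end and 54% and 87% at the high end.

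**Patients wholly outside the trigger.** Section 3.5.6 puts surgery 14 to 42 days after Visit 2. If inclusion is counted at Visit 2, anyone included in the last two weeks is operated on and followed entirely after closure. If inclusion is counted at surgery, nobody is.

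**How often five would be reached.** Take 7.1% as the probability per patient over full follow-up. The documents describe it as a rate over many years, so this is an assumption. Then P(X ≥ 5) for a binomial with n = 55 and p = 0.071 is 0.352, about 35%. As an illustration only, with a constant hazard and the base schedule, the chance of reaching five before closure is 12% at 7.1%. At 9.1% it is 25%, against 57% over full follow-up, with 3.4 of 5.0 expected events occurring by closure.

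**The case against.** The strongest reply is that little actually stops, and most of it stands. Section 3.5.5.2 defines SAE and major complication together, so under 3.6.5 each major complication still reaches the DSMB. The sponsor is told within 24 hours (4.5.13). Fatal or life-threatening events go to authorities and ethics committees within seven days and other unanticipated serious events within fifteen (4.5.15). Explanted devices are returned, tested and reported to the local authority (3.5.5.2). Termination for safety remains open (3.6.7). A reader might infer that nothing is triggered after closure, or that a late cluster would come to light only in the final report. The documents do not support either reading.

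A reader might also take 3.6.6 as an independent rule with no cut-off that contradicts 3.6.4. It refers back to 3.6.4, so it may simply inherit the time limit. The general power in 3.6.7 can coexist with a time-limited DSMB trigger. The firmer tension is within 3.6.4, between its open-ended cumulative count and its last sentence, and with the threshold clause in 3.6.5.

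Three further points have force. Person-time is not risk: if major complications cluster around surgery, the share of events after closure is smaller, and the documents give no hazard shape and no timing for the risks in 4.2. Linking the trigger to enrolment is a recognisable choice if its purpose is to halt enrolment. Finally, assessment frequency and action rules are placed in a data safety monitoring plan that is not among the documents reviewed, so periodic DSMB meetings after closure cannot be ruled out. That plan could add reviews, but the protocol's express sentence would still need changing.

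**Conclusion.** The concern holds in a limited form. The protocol states, rather than merely leaves open, that the required DSMB meeting on the accumulated count ends when inclusion closes. That does not fit a first-year endpoint with a limit computed on all 55 patients, nor the open-ended count at the start of 3.6.4. What lapses is the obligation to meet and decide; event reporting and the power to terminate continue.

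Under uniform accrual, roughly a quarter to a third of post-operative follow-up lies outside the trigger, and just over half to nearly two thirds of patients still have follow-up left. That majority is not assured: it fails under declining accrual. The figures measure exposure, and the share of events could be lower. The estimate of the major-complication rate and its confidence interval are unaffected, because no test or decision rule in the analysis depends on this meeting. This is a correction to safety oversight that should be made. The differing wording of the limit across 3.6.4 and 3.6.5 (beyond five, at the fifth, more than four) is a separate matter.

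**What to change.** Reconcile section 3.6.4 with 3.6.5 to 3.6.7:

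- In 3.6.4 and 3.6.5, let the trigger for the extraordinary DSMB meeting run from the first surgery to the last subject's final visit.
- Delete the closing sentence of 3.6.4, or qualify it so that it no longer commits the study to completion whatever the count.
- In 3.6.5, state whether the threshold clause applies after inclusion closes.
- State that any action after closure is for the DSMB to decide. No change to the limit is proposed here.

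The cost is protocol wording and at most one additional ad hoc meeting of the existing board. The sponsor should accept knowingly that, with the count left at five, the meeting would be called about 35% of the time over full follow-up even if the true rate were the literature's 7.1%. A meeting would therefore not by itself be evidence of excess risk.

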### **3.6.5 Data and Safety Monitoring Board**

Each SAE will be submitted to the DSMB.

If more than 4 major complications are reached during the inclusion period, an extraordinary meeting of the DSMB will take place within the 7 calendar days.

The DSMB shall be notified each time an SAE occurs. Monitoring of key safety endpoints will be conducted as described above, and if rates significantly exceed pre-set thresholds, Competent Authorities will be notified and information supplied to the DSMB.

DSMB's Policies are described in the Oticon Medical Manual Procedures (composition/organization).

The data safety monitoring plan, describe:

- Type of data or events captured under the monitoring plan
- Names of persons who will be responsible for monitoring the data collected
- The frequency of assessments/analysis of data or events captured by the monitoring plan (e.g. periodic time interval, or after a specific number of participants are enrolled)
- Time frame for reporting unanticipated issues, adverse effects, protocol deviations, protocol violations
- Definition of specific events or stopping rules dictating when some actions are required
- Procedure and timeframes for communication outcomes of monitoring reviews to investigator sites, EC and CAs.
- Plans to monitor adherence to the EC/CA-approved protocol and assure the validity and integrity of data.

The DSMB should also assess the performance of overall operation study.

### **3.6.6 Early Stopping Rules**

No statistical stopping rule for success is applied for the primary efficacy endpoint.

If no interim analysis shows safety endpoint values greater than the pre-set limit, the study shall continue until completion (Please refer to section 3.6.4).

### **3.6.7 Study Interruption or Withdrawal**

Premature termination of this clinical trial may occur because of regulatory authority decision, change in opinion of the EC/CA, safety problems, or at the discretion of Oticon Medical. In addition, Oticon Medical retains the right to discontinue the trial at any time.

If a trial is prematurely terminated or discontinued, Oticon Medical will promptly notify the PI. After notification, the PI must contact all participating subjects within 24 hours. As directed by Oticon Medical, all trial materials must be collected and all CRFs completed to the greatest extent possible.

## 4. RISK ANALYSIS

### 4.1 Expected clinical benefits

The Neuro CIS has many similar features to the previous CIS (Digisonic SP + Saphyr SP Neo) and incorporate some of the same technologies. The two principle new features implemented into the Neuro Zti implant are the removable magnet and the ECAP recording hardware. These 2 features are currently incorporated into FDA approved CISs. The new features implemented in the Neuro One processor are related to hearing aid technology integration for signal processing (integration of directional microphones, etc.), but coding strategy and stimulation principles are similar between the Neuro CIS and the Digisonic CIS.

Expected clinical benefits are comparable to other CIS systems available on the market: for example Bergeron et al. [28] compared devices with the most recent technologies using HINT tests and showed an improvement of Digisonic SP + Saphyr Neo CIS compared to competitors in quiet and some noisy conditions (+10dB SNR), and similar performance in other noisy conditions among all devices..

### 4.2 Anticipated Adverse Events

#### Risks of general anesthesia

- **General anesthesia.** Individuals may react differently to anesthesia. Although the risk associated with general anesthesia to obtain a cochlear implant is outweighed by the potential benefit for most candidates, individuals with certain medical conditions may be at higher risk for complications.

#### Risks of cochlear implant surgery

- **Injury to the facial nerve.** The facial nerve traverses through an anatomical region near the cochlea to provide movement to the muscles of the face. The nerve lies close to where the surgeon needs to place the implant and may be injured during surgery. An injury to the nerve may cause a temporary or permanent weakening or even full paralysis on the same side of the individual face as the implant.
- **Meningitis.** This condition results from an infection that results in inflammation of the meninges that line the central nervous system. Meningitis may result in serious complications including permanent brain damage or death. Individuals who experience inner ear structure anomalies or malformations and/or are implanted with a cochlear implant may be at an increased risk of meningitis.
- **Cerebrospinal fluid leakage.** The brain and central nervous system are surrounded by fluid that may leak from a hole created in the inner ear during surgery. An uncontrolled leak of CSF may result in serious injury or death.
- **Perilymph fluid leakage.** The inner ear contains a fluid called perilymph. This fluid, which is continuous with CSF, may leak through a hole created for electrode array placement.
- **Infection** of the wound or the implant. This includes the risk of otitis media which may cause infection on the implant either outside the cochlea or within the ear. In the case of infection that cannot be resolved with antibiotics, the device may need to be explanted to resolve the infection.
- **Skin flap issues.** Although this will typically resolve with treatment, in the worst case the device may need to be explanted, with re-implantation once the infection has resolved.
- **Cholesteatoma** formation.

- **Blood or fluid collection/edema** at the site of the surgery
- **Vertigo or dizziness**
- **Tinnitus**
- **Taste disturbance.** The sensory nerve that conveys taste sensations from the tongue also passes through the middle ear and may be injured during the surgical procedure.
- **Stiffness or Numbness** in the area around the surgical site
- **Reparative granuloma.** Is the result of localized inflammation and may occur if the body rejects the implant.
- **Pain.**
- Unforeseen complications due to the surgical procedure
- Unforeseen complications that could occur with long term implantation that cannot be predicted beforehand

### **Risk associated with the device**

A study participant:

- May have skin irritation or redness behind the ear. Removal of the sound processor is recommended until the issue is resolved.
- May have skin irritation or redness in and around the implanted area. A magnet holds the antenna in place against the skin on the implanted device. Reduction in the magnet strength is recommended.
- May have to undergo device explanation if an infection occurs after the implant surgery that cannot be resolved with antibiotics. This is a rare complication.
- May have the sensation of heat or burning due to an increase in the processor temperature. The individual may remove his/her processor immediately.
- May experience an uncomfortably loud sensation. The T and C level thresholds are based on each individual's responses during the fitting session.
- May remove the processor before medical examinations and treatments; radiotherapy, MRI, ultrasound, scan, treatment using electric currents.
- May be able to undergo some medical examinations and treatments with caution and under specified conditions:
  - MRI imaging at 3 Tesla may be obtained with implant magnet removal. A minor surgery is required to remove the magnet beforehand. The implant is 1.5T compatible, however, if the medical region of interest falls within the projected artifact produced by the implant, the magnet may be removed to minimize artifacts.
  - Neurostimulation, when not directly over the implant.
  - Electrical surgery. Monopolar electrosurgical instruments may not be used on the head or neck area during and following implant placement.
  - Ionic radiation therapy.
  - Electrotherapy may be not used on the head and neck area.
  - Diathermy may be not used on the head and neck area.
  - Defibrillation may cause device damage but may be used in life-threatening situations.
- May be not able to have electroconvulsive therapy.
- May lose residual hearing. The implant may damage any remaining hearing in the implanted ear.

- May be at risk for dislocation and/or migration and/or demagnetization of the implanted magnet through a strong magnet field, or other conditions such as exposure to an MRI scan. Such conditions may require revision surgery to replace the magnet.
- May be at risk for electrode array misplacement. This is a rare and correctable complication that may require revision surgery to re-insert and secure the electrode. To further mitigate this risk, final electrode position is confirmed by visual inspection prior to closing and inferred by impedance and ECAP measures at the end of surgery.
- May exhibit device rejection which may result in the extrusion of the implanted components and/or necessitating the need for device removal.
- May be at risk for the electrode array being damaged during surgery.
- May be at risk for electrode post-surgical electrode migration requiring revision surgery to re-insert and secure the electrode.
- May experience an internal device failure. The individual would need to undergo additional surgery to resolve this issue and be exposed to additional surgical risk.
- May develop the need to have the CIS removed for medical reasons.
- May be at risk for impact or trauma near the implanted components resulting in partial or complete failure of the implanted components. Accidents, slips, trips, falls, contact sports, and any external impact may increase the risk of damage to the implant. Device failure would require revision surgery for correction.

